5.11 Packaging, Labeling, and Storage

The ALRN-6924 study vials will be labeled according to the local law and legislation. A copy of the labels will be filed and stored in the trial master files and can be made available to the study sites upon request.

ALRN-6924 for Injection is stored as frozen product at -15° to -25° C or refrigerated product at 2° to 8° C.

Palbociclib should be stored as described in the current approved US prescribing information.

5.12 Drug Accountability

The Principal Investigator is responsible for ensuring accountability for the investigational agent ALRN-6924, including reconciliation of drugs and maintenance of drug records.

Upon receipt of ALRN-6924, the clinical study site will check for accurate delivery and acknowledge receipt by signing (or initialing) and dating the documentation provided and returning it to the Sponsor or Sponsor's designee. A copy will be retained in the Investigator site file.

The receipt, dispensing, administration, and return of ALRN-6924 will be recorded on the appropriate drug accountability forms, and an accurate accounting will be available for verification by the Sponsor monitor at each monitoring visit.

Investigational agent accountability records will include:

- Confirmation of delivery to the site
- Inventory at the site
- Dispensing for each patient
- Return or alternative disposition of unused study drug
- Dates, quantities, batch numbers, expiry dates, and the Patient Identification Number for the study.

The Sponsor monitor will periodically review the investigational agent accountability forms to verify drug accountability and compliance. Drug accountability and destruction instructions are outlined in the Pharmacy Binder.

6 STUDY PROCEDURES

6.1 Schedule of Study Events

The schedule of study activities (including assessments, tests, exams, disease assessments, collection of tissue specimens, and study drug administration) beginning with molecular screening and continuing throughout the study are provided in the appendices starting with [Appendix C](#).

Phase 1 dose escalation: During the first 2 dose levels, patients will receive ALRN-6924 on Days 1, 8, and 15 of a 28-day cycle. Starting with DL 3, patients in treatment DR-A and DR-A-2 (starting at DL7) will continue being treated once a week on Days 1, 8, and 15 of a 28-day cycle, whereas patients in DR-B will be treated twice a week, on Days 1 and 4, 8 and 11 of a 21-day cycle. Dose escalation proceeds based on safety parameters and review as described in Sections 5.5.3, 5.6, and 8.10.1 and each DR is independent of each other. All data regardless of DR and DL will be collated and available for each Safety Review Meeting.

Phase 2a dose expansion:

- Patients with PTCL: up to 3 single agent dosing regimens will be tested: DR-A (Days 1, 8, and 15 of a 28-day cycle); DR-B (Days 1, 4, 8, and 11 of a 21-day cycle); and DR-C (Days 1, 3, and 5 of a 21-day cycle).
- Patients with MDM2 amplified or MDM2/CDK4 co-amplified solid tumors: ALRN-6924 (DR-A) will be administered in combination with palbociclib in a 28-day cycle (see [Appendix I](#) and [Appendix J](#)).

Refer to the Pharmacy Binder for detailed instructions on how to prepare and administer ALRN-6924. For instructions on administration of palbociclib, refer to the current approved US prescribing information.

6.2 Informed Consent and Pediatric Assent

Informed consent will be collected prior to any study specific procedures. This may be accomplished by using an Informed Consent Form (ICF) specific to molecular screening followed by an ICF for the main study, or may be a combined form covering both molecular screening and the main study.

For any cohort in which adolescents are eligible to enroll, pediatric assent may be required in accordance with local laws and regulations. Informed consent must be provided by a legally-acceptable representative if the age of majority has not been reached. A minor who reaches the age of majority during study participation must be reconsented to confirm their agreement with continued participation.

6.3 Biopsies

A fresh or archival biopsy taken pre-dose must be sent to the central laboratory for TP53 and/or MDM2 and CDK4 amplification testing. See Section 3.2 and the Laboratory Manual for details. For patients in the PTCL expansion cohorts, an additional pre-treatment tumor sample is required to be available for central pathology read (if requested).

In the Phase 2a EXP PTCL cohorts, optional biopsies will be taken for PD purposes as well as for TP53 testing: during screening, during treatment, and at times of suspected progression. In the palbociclib combination cohort, if a biopsy is taken for any reason during the study, the samples may be used for further analysis. See the Laboratory Manual for details. Samples might be submitted for whole exome sequencing (with paired germline samples) and RNA sequencing (RNAseq), and results will be compared

between pre-treatment and on-treatment, and times of suspected progression. Tumor samples will be examined for markers of disease response and resistance. Protein expression via immunohistochemistry and RNA expression via quantitative RT-PCR may be examined on specimens obtained prior to beginning treatment, during treatment with ALRN-6924, and then upon suspected progression.

6.4 Germline DNA

To be collected via a buccal swab only for patients in Phase 2a EXP PTCL cohorts who consent to optional biopsies. See the Laboratory Manual for details.

6.5 Medical and Disease History

The medical history is to include demographic information, cancer history, including disease duration, previous treatment regimens, and toxicities, as well as information about the patient's non-malignancy-related history and all prior surgeries.

6.6 Vital signs

Includes blood pressure, pulse, respiration rate, and body temperature. Collection times are indicated in the schedule of events. Additional vital signs will be collected at the discretion of the investigator.

6.7 Electrocardiograms

Screening and predose ECGs (if required) are to be performed in triplicate (5-10 min between readings). ECGs are to be performed after the patient has been supine for at least 10 minutes. All ECGs should be performed with the patient in the same physical position. Postdose ECGs (if required) are to be performed in triplicate (5-10 min between readings) only if patient has a QTc that is a) >500 msec; b) increased by 60 msec over pre-dose; or c) decreased by 50 msec below pre-dose recording.

6.8 Physical Examination

Full physical examination to be performed at Screening, Day 1 pre-dose, and End of Treatment; all other physical examinations (if required) may be symptom-directed. Weight to be collected at Screening and on Day 1 (or up to 3 days prior to Day 1) of each cycle. Height is to be obtained only at the Screening visit.

6.9 Laboratory Assessments

Laboratory assessments to be performed locally may include:

- Clinical chemistry (glucose, calcium, albumin, total protein, sodium, potassium, CO₂, chloride, phosphate, BUN [blood urea nitrogen], serum creatinine, uric acid, alkaline phosphatase, ALT, AST, LDH, total and direct bilirubin).
- Hematology (complete blood count, platelets and differential).
- Urinalysis (dipstick measurement [pH, specific gravity, protein, glucose, ketones, nitrite, leukocyte esterase] with microscopic analysis, if results of the dipstick indicate additional testing required).
- Coagulation (PT, INR, aPTT).
- Serum or urine pregnancy test (Beta human chorionic gonadotropin [β -hCG]) for women of child-bearing potential.

- At select visits, lymphocyte subset testing will be performed (B-cells, T-cells including CD4 and CD8, natural killer [NK] cells).
- C-reactive protein, fibrinogen, and reticulocytes will also be collected at select visits.
- HPV testing of tumor tissue from cancers likely to be HPV-positive: to be performed dependent upon cancer type, including (but not limited to) cervical cancer, oropharyngeal cancer, head and neck squamous cell cancers or anal cancer.
- HIV, Hepatitis B and C testing

6.11 Concomitant Medications

Concomitant medications (current medications and those taken within 28 days of Cycle 1, Day 1) through the end of treatment visit or until start of subsequent anticancer therapy.

6.12 PK and PD Assessments

Refer to the Laboratory Binders for specimen collection, processing, storage, and shipment procedures.

Blood samples for PK and PD assessments will be collected at the timepoints shown in the tables below. Patients who are already enrolled in the expansion and consent to this testing will have blood drawn at their next available cycle (i.e. if the next available cycle is Cycle 4, they will follow the PK/PD Cycle 1 testing at Cycle 4 [with the exception of germline DNA and cfDNA testing which remains on the below schedule], and will follow the below indicated Cycle 2 testing at Cycle 5).

DR-A, DR-A-2 (ALRN-6924 single agent therapy)

Screening		PK	PD
During screening			cfDNA
Cycle 1		PK	PD
Day 1	within one hour before start of infusion (SOI)	X	MIC-1 CTC (select sites only) Germline DNA (EXP only)
	End of Infusion (EOI) (+5 min)	X	
	30 min after EOI (\pm 5 min)	X	
	1 hr after EOI (\pm 5 min)	X	
	2 hr after EOI (\pm 10 min)	X	
	4 hr after EOI (\pm 10 min)	X	MIC-1 CTC (select sites only)
	8 hr after EOI (\pm 2 hours)	X	MIC-1 CTC (select sites only)
Day 2	24 hours (\pm 4 hr) after SOI day prior	X	MIC-1 CTC (select sites only)
Day 3 (DEP only)	48 hours (\pm 4 hr) after SOI	X	MIC-1
Cycle 2		PK	PD
Day 15	EOI (+5 min)	X	
	1 hr after EOI (\pm 5 min)	X	
	4 hr after EOI (\pm 10 min)	X	
Day 16 (DEP only)	24 hours (\pm 4 hr) after SOI day prior	X	
Cycle 5		PK	PD
Day 1	within one hour before SOI		cfDNA
End of Treatment		PK	PD
End of Treatment			cfDNA

DR-B (ALRN-6924 single agent therapy)

Screening		PK	PD
During screening			cfDNA
Cycle 1		PK	PD
Day 1	within one hour before SOI	X	MIC-1 CTC (select sites only) Germline DNA (EXP only)
	EOI (+5 min)	X	
	30 min after EOI (\pm 5 min)	X	
	1 hr after EOI (\pm 5 min)	X	
	2 hr after EOI (\pm 10 min)	X	
	4 hr after EOI (\pm 10 min)	X	MIC-1 CTC (select sites only)
	8 hr after EOI (\pm 2 hours)	X	MIC-1 CTC (select sites only)
Day 2	24 hours (\pm 4 hr) after SOI day prior	X	MIC-1 CTC (select sites only)
Day 3 (DEP only)	48 hours (\pm 4 hr) after SOI	X	MIC-1
Day 4	within one hour before SOI	X	MIC-1
Cycle 2		PK	PD
Day 11	EOI (+5 min)	X	
	1 hr after EOI (\pm 5 min)	X	
	4 hr after EOI (\pm 10 min)	X	
Day 12 (DEP only)	24 hours (\pm 4 hr) after SOI day prior	X	
Cycle 5		PK	PD
Day 1	within one hour before SOI		cfDNA
End of Treatment		PK	PD
End of Treatment			cfDNA

DR-C (ALRN-6924 single agent therapy)

Screening		PK	PD
During screening			cfDNA
Cycle 1		PK	PD
Day 1	within one hour before SOI	X	MIC-1 Germline DNA CTC (select sites only)
	EOI (+5 min)	X	
	30 min after EOI (\pm 5 min)	X	
	1 hr after EOI (\pm 5 min)	X	
	2 hr after EOI (\pm 10 min)	X	
	4 hr after EOI (\pm 10 min)	X	MIC-1 CTC (select sites only)
	8 hr after EOI (\pm 2 hours)	X	MIC-1 CTC (select sites only)
Day 2 (optional)	24 hours (\pm 4 hr) after SOI day prior		MIC-1 CTC (select sites only)
Day 3	within one hour before SOI	X	MIC-1
	EOI (+5 min)	X	
Day 5	within one hour before SOI	X	MIC-1
	EOI (+5 min)	X	
	1 hr after EOI (\pm 5 min)	X	
	2 hr after EOI (\pm 10 min)	X	
Day 8	Any time	X	MIC-1
Cycle 2		PK	PD
Day 5	within one hour before SOI	X	
	EOI (+5 min)	X	
	1 hr after EOI (\pm 5 min)	X	
	2 hr after EOI (\pm 10 min)	X	
Cycle 5		PK	PD
Day 1	within one hour before SOI		cfDNA
End of Treatment		PK	PD
End of Treatment			cfDNA

ALRN-6924 plus palbociclib

Timepoint	PK		PD
	ALRN-6924	Palbociclib	
During screening			cfDNA
Cycle 1			
Day 1	within one hour before start of ALRN-6924 infusion (SOI)	X	
	End of Infusion (EOI) (+5 min)	X	
	30 min after EOI (\pm 5 min)	X	
	1 hr after EOI (\pm 5 min)	X	
	2 hr after EOI (\pm 10 min)	X	
	4 hr after EOI (\pm 10 min)	X	
Day 2	24 hrs (\pm 2 hr) after EOI Day 1/ 18 hrs (\pm 2 hr) after Day 1 palbociclib dose	X	X
Day 8	within one hour before ALRN-6924 SOI	X	X
	EOI (+5 min)	X	X
Day 15	within one hour before ALRN-6924 SOI	X	X
	EOI (+5 min)	X	X
Day 22	Any time	X	X
Cycle 5			
Day 1	within one hour before SOI		
End of Treatment			
End of Treatment	Any time		cfDNA

6.13 End of Treatment and End of Study

Approximately 30 days (+/- 5 days) after the last dose of study drug, an end of treatment visit will be conducted. For patients in Phase 1, this visit will be the same as the end of study. Patients in Phase 2 will remain on study and be followed for survival and subsequent therapies.

7 STATISTICAL CONSIDERATIONS

Full details will be included in the Statistical Analysis Plan.

7.1 General Considerations

The primary objectives of this Phase 1/2a study are to determine the MTD or OBD and DLT(s) of ALRN-6924 administered by IV infusion on Days 1, 8 and 15 (DEP DR-A and DR-A-2) of a 28-day cycle or Days 1, 4, 8, 11 (DEP DR- B) of a 21-day cycle, in patients with advanced solid tumors or lymphoma and to further investigate the clinical safety profile and efficacy of ALRN-6924 (administered alone or in combination with other agents) in expansion cohorts (Phase 2a) which will include an additional dosing cohort of ALRN-6924 administered by IV infusion on Days 1, 3, and 5 (DR- C) of a 21-day cycle. Statistical analyses will be descriptive in nature and will account for all dose levels and regimens studied. Where applicable, analyses will include a description of adolescent versus adult data.

7.2 Patient Disposition and Characteristics

The baseline characteristics of patients enrolled will be summarized. All patients who received study treatment will be accounted for, including patients who died or withdrew from study treatment during the study.

7.3 Safety Analysis

The safety population will include all patients who have received at least one dose of ALRN-6924. Adverse events, vital sign measurements, clinical laboratory information and concomitant medication usage will be tabulated. All toxicities will be summarized by severity based on the NCI CTCAE version 4.03 and relationship to treatment. Serious adverse events will be listed separately. Graphical displays will be provided where useful in the interpretation of results. Statistical analyses will be descriptive in nature and will account for all dose levels and regimens studied.

7.4 Pharmacokinetic Analysis

Levels of ALRN-6924 and its metabolite (and other agents given in combination with ALRN-6924) will be measured in blood samples collected at specific timepoints. Pharmacokinetic data will be tabulated and summarized by individual patient and collectively by dose level for each dose regimen. Graphical displays will be provided where useful in the interpretation of results.

7.5 Pharmacodynamic Analysis

Levels of p53, MDM2, MDMX, p21 and caspase will be measured in tumor specimens collected before beginning treatment, during Cycle 1 or Cycle 2 and at suspected disease progression. MIC-1 and CTCs will be measured in blood samples. Pharmacodynamic effects on the composition of cell free DNA from blood will be evaluated. Pharmacodynamic data will be tabulated and summarized by individual patient and collectively by dose level. Graphical displays will be provided where useful in the interpretation of results.

7.6 Clinical Activity Analysis

To evaluate clinical activity, response rates and duration of response based on RECIST 1.1, IWG 2014, RANO, iRECIST, or other appropriate or exploratory criteria will be analyzed.

In DEP, the efficacy evaluable population will consist of patients who:

- Received at least one dose of ALRN-6924 at a dose level at least 0.8 mg/kg per infusion
- Have at least one post-baseline evaluation or had clinical progression and
- Are TP53 wild type or indeterminate (as assessed by the central lab, and if not assessed by central laboratory, as assessed by the local laboratory)

In the single agent EXP cohorts, the efficacy evaluable population will consist of patients who:

- Received at least one dose of ALRN-6924
- Have at least one post-baseline evaluation or had clinical progression and
- Are TP53 wild type (as assessed by the central lab)

In the EXP cohort of patients with MDM2 amplified or MDM2/CDK4 co-amplified solid tumors, the efficacy evaluable population will consist of patients who:

- Received at least one dose each of ALRN-6924 and palbociclib
- Have at least one post-baseline evaluation or had clinical progression and
- Are confirmed to have MDM2 amplification (with or without CDK4 co-amplification) with TP53 and Rb wild type (as assessed by the central lab)

A descriptive analysis of other evidence of anti-tumor activity or other clinical benefit will be provided based on clinical, radiographic or other appropriate assessment of efficacy or clinical anti-tumor activity.

Overall response rate, duration of response, and time to response will be assessed in DEP as well as in EXP.

Additional clinical activity analyses in the Phase 2a dose expansion will include OS and PFS and OS at 1 year. Time-to-event endpoints will be calculated from the time of first administration of ALRN-6924 (Day 1) until the stated event or end of study.

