- Levels of biomarkers (e.g., p53, MDM2, and MDMX gene sequence and copy number, as well as p21 RNA and/or protein expression) in tumor biopsy samples, and in blood, CTCs, where detectable, or MNC samples
- Incidence of anti-ALRN-6924 antibodies

Study Endpoints – Phase 2a dose expansion in MDM2 amplified or MDM2/CDK4 co-amplified solid tumors (ALRN-6924 plus palbociclib)

Primary endpoints:

- The proportion of efficacy-evaluable patients who achieve complete response (CR) or partial response (PR), per investigator assessment, in accordance with RECIST 1.1 or iRECIST (for solid tumor patients) or Response Assessment in Neuro-Oncology (RANO) criteria (for glioblastoma patients).
- Safety and tolerability including the occurrence of adverse events (AEs) and serious adverse events (SAEs), and changes from baseline in vital signs, laboratory analytes, and physical examination findings

Secondary endpoints:

- PK parameters, including AUC, C_{max} , T_{max} , and $t_{1/2}$ for ALRN-6924, its metabolites, and palbociclib
- The median time, in months, from the first response of CR or PR to disease progression or death from any cause (DOR)
- The median time, in months, for each of the following:
 - The first dose of ALRN-6924 to the first response of CR or PR (TTR)
 - The first dose of ALRN-6924 to disease progression or death from any cause (measured at 1 year and beyond) (PFS)
 - The first dose of ALRN-6924 to death from any cause (measured at 1 year and beyond) (OS)

Exploratory endpoint:

- The correlation of response with MDM2, MDMX, and/or CDK4 gene copy number and other genetic and protein biomarkers

Study Design

This is a Phase 1/2a open-label, multi-center, dose-escalation and dose expansion study designed to evaluate the safety, tolerability, PK, PD, and anti-tumor effects of ALRN-6924 administered by IV infusion using up to 4 different dosing regimens of a 28- or 21-day cycle (alone or in combination), in patients with advanced solid tumors or lymphomas with WT TP53 (see p53 Status Determination below). In Phase 1 and Phase 2a, patients will receive ALRN-6924 either once weekly for three consecutive weeks for a 28-day cycle (1 and 2 hour infusions may be tested) or twice weekly for two consecutive weeks for a 21-day cycle. In Phase 2a, dosing three times a week for one week over a 21-day cycle will be tested.

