4.2 Duration of Overall Response

The duration of overall response is measured from the time measurement criteria are met for CR or PR (whichever is first recorded) until the first date that recurrent or progressive disease is objectively documented (taking as reference for progressive disease the smallest measurements recorded since the treatment started).

The duration of overall CR is measured from the time measurement criteria are first met for CR until the first date that recurrent disease is objectively documented.

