4.2. CLINICAL ACTIVITY ENDPOINTS

- Overall response - objective evidence of complete response (CR) or partial response (PR). The evaluation of overall response will be based on response, as determined by the investigator, in accordance with RECIST version 1.1, for subjects with solid tumors, or IWG 2014 criteria, for subjects with lymphomas.

- Overall Response Rate (ORR) - proportion of subjects with overall response
- Time to Response (TTR) - time from the date of the first dose of ALRN-6924 to the date of the first documentation of overall response. The TTR will be calculated as follows (in months):

$$(\text{date of first response (CR/PR)} - \text{first dose date} + 1)/30$$

Subjects who do not respond will be censored at their last tumor assessment.

- Duration of Response (DOR) - time from the first documentation of overall response to the first documentation of objective or clinical disease progression or death due to any cause. This endpoint is only assessed among subjects who achieve overall response at some point during the study. The DOR will be calculated as follows (in months):

$$(\text{date of disease progression/death} - \text{date of first response (either CR or PR)} + 1)/30$$

Version V.1

Subjects who do not have disease progression (or death) will be censored at the last known time point that the subject was progression-free. Subjects with two or more consecutive missing response assessments prior to a visit with progression (or death) will be censored at the last date of tumor assessment when the subject was known to be progression free.

- Disease control - objective evidence of CR, PR, or stable disease (SD). The evaluation of disease control will be based on response, as determined by the investigator, in accordance with RECIST version 1.1, for subjects with solid tumors, and IWG 2014 criteria, for subjects with lymphomas.
 - Disease Control Rate (DCR) - proportion of subjects with objective evidence of disease control
 - Duration of Clinical Benefit (DCB) - time from the first documentation of disease control to the first documentation of objective or clinical disease progression or death due to any cause. This endpoint is only assessed among subjects who achieve disease control at some point during the study. The DCB will be calculated as follows (in months):

(date of disease progression/death - date of first response (either CR/PR/SD) + 1)/30

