Subjects who do not have disease progression (or death) will be censored at the last known time point that the subject was progression-free. Subjects with two or more consecutive missing response assessments prior to a visit with progression (or death) will be censored at the last date of tumor assessment when the subject was known to be progression free.

- Best Overall Response (BOR) - the highest level of objective response recorded (complete response, partial response, stable disease, or progressive disease) for each subject
- Progression-free Survival (PFS), defined as the time from the date of the first dose of ALRN-6924 to the date of first evidence of objective or clinical disease progression or the date of death, due to any cause, whichever occurs first. The PFS will be calculated as follows (in months):

(date of disease progression/death - first dose date + 1)/30

Subjects who do not have disease progression (or death) will be censored at the last known time point that the subject was progression-free. Subjects with two or more consecutive missing response assessments prior to a visit with progression (or death) will be censored at the last date of tumor assessment when the subject was known to be progression free.

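### For Phase 2a, Protocol 7.6 as written starts the DOR clock at first dose and runs event-free PFS to end of study, past the last scan

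*Protocol*

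**What the plan says.** The rule at issue closes Protocol 7.6: "Time-to-event endpoints will be calculated from the time of first administration of ALRN-6924 (Day 1) until the stated event or end of study". It directly follows a sentence naming OS and 1-year PFS and OS as additional Phase 2a analyses. Shortly before that, the same section says: "Overall response rate, duration of response, and time to response will be assessed in DEP as well as in EXP".

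Other places define DOR from response:

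- Combination-cohort secondary endpoints (Protocol synopsis): "The median time, in months, from the first response of CR or PR to disease progression or death from any cause (DOR").
- Protocol Appendix K (RECIST 1.1), item 4.2: "The duration of overall response is measured from the time measurement criteria are met for CR or PR (whichever is first recorded").
- SAP 4.2: "time from the first documentation of overall response to the first documentation of objective or clinical disease progression or death due to any cause".

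SAP 4.2 also handles patients without an event: "Subjects who do not have disease progression (or death) will be censored at the last known time point that the subject was progression-free". It adds a missed-assessment rule: "Subjects with two or more consecutive missing response assessments prior to a visit with progression (or death) will be censored at the last date". The date meant is that of the latest scan still showing no progression. SAP 3.1, however, confines that document to Phase 1 and promises a separate plan for Phase 2a.

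On follow-up, Protocol 6.13 makes end of study coincide with the end-of-treatment visit for Phase 1, but says of the expansion: "Patients in Phase 2 will remain on study and be followed for survival and subsequent therapies". Appendices D, F, H and J describe that follow-up as phone or other contact about every 2 months, with no imaging in the long-term follow-up column.

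**The concern.** DOR measured from first dose is not a duration of response: it adds the time to response to it. PFS that runs to end of study in patients nobody is scanning treats absence of information as absence of progression.

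Both errors favour the drug, and they fall on stated Phase 2a objectives: DOR, PFS and PFS at 1 year. Up to three PTCL regimens are to be tested to find the best one. If the regimens differ in how many patients stop for toxicity or by choice, the PFS bias will differ between them. Because the first scan falls at different times under different regimens, the amount added to DOR can differ too.

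**Working it through.** **1. Which rule governs which cohort.** The plan has no sample-size or power figure that depends on this sentence, so there is none to reproduce. The check starts with the definitions.

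| Cohort | DOR origin | Event-free PFS/DOR ends at |
|---|---|---|
| Phase 1 | First response (SAP 4.2) | Last progression-free time point (SAP 4.2) |
| Combination, Phase 2a | First CR/PR (synopsis), against first dose (7.6) | End of study (7.6) |
| PTCL, Phase 2a | First dose (7.6); no other definition supplied | End of study (7.6) |

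For PTCL, the endpoint list speaks only of anti-tumor effect in general, and Appendix L gives Lugano staging and response categories without a duration definition. Appendix K covers solid tumors. The only other censoring rule in the protocol, in 5.10.2, concerns permitted concurrent surgery or radiation.

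**2. Size of the DOR error.** Excess = time from first dose to first response. Protocol 6.10 puts the first scan before Cycle 3 (28-day cycles) or before Cycle 4 (21-day cycles). Using the SAP's 30-day month:

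- DR-A and combination: 2 × 28 = 56 days; 56/30 = 1.87 months.
- DR-B and DR-C: 3 × 21 = 63 days; 63/30 = 2.10 months.

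Example: response on Day 57, progression on Day 225. From response, (225 − 57 + 1)/30 = 5.63 months. From first dose, (225 − 1 + 1)/30 = 7.50 months. The difference is 1.87 months.

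These are typical values, not minimums. Appendices F and H allow imaging any time after the last Cycle 3 dose, which is Day 42 + 11 = 53 in DR-B and Day 42 + 5 = 47 in DR-C. Later responders have a larger excess.

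**3. Size of the PFS error (simulation).**

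- From the documents: scans every 56 days; about 8 months of follow-up after the last enrollment (3.4); an end-of-treatment tumor assessment if none was done in the prior 6–8 weeks (6.10); death counted as a PFS event.
- Assumed: exponential PFS with median 91 days; 8-month accrual; 10%, 20% or 30% stopping without progression at times uniform on Days 14–112; median post-progression survival 6–12 months.
- True 48-week PFS: 2^(−336/91) = 0.077.

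| Stopping without progression | Censored at last progression-free scan | 7.6 as written |
|---|---|---|
| 10% | about 0.08 | 0.10–0.11 |
| 20% | about 0.08 | 0.13–0.14 |
| 30% | about 0.08 | 0.15–0.17 |

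The exact handling of the end-of-treatment scan moves the top value by about 0.01, to 0.18. In a cohort of 20, the excess is (0.10 − 0.08) × 20 = 0.4 to (0.17 − 0.08) × 20 = 1.8 patients.

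**4. Sensitivity to the assumed median.** A second simulation counted deaths but had no end-of-treatment scan, so it leans high. It assumed 10–30% loss of scans, post-progression survival of 6 or 12 months, and 8–32 months from first dose to study end. One-year PFS:

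| True median | 7.6 as written | SAP 4.2 rule | Truth |
|---|---|---|---|
| 2 months | 7.3–26.0% | 1.3–2.0% | 1.6% |
| 4 months | 18.2–31.3% | 13.0–14.2% | 12.5% |
| 6 months | 30.0–39.2% | 26.4–27.5% | 25.0% |

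The estimated median was identical under the two rules in 15 of the 18 scenarios; the three exceptions all had 30% loss. The bias sits in the late part of the curve.

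**The case against.** The sentence shares a paragraph with OS and PFS, for which first dose is the correct origin, while DOR and TTR have their own paragraph. Every explicit DOR definition supplied starts at response. Protocol Section 7 leaves full details to the SAP, and a Phase 2a SAP is still to come; the Phase 1 SAP already gets both points right. The analyses are descriptive, with no test or go/no-go rule built on DOR or PFS.

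Much of this stands, and it rules out several stronger readings:

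- A reader might infer that DOR is wrong throughout the trial. It is not: SAP 4.2 governs Phase 1, and the combination cohort has a correct definition, which makes the problem there an internal contradiction.
- A reader might infer that unscanned Phase 1 patients are also carried forward as progression-free. SAP 4.2 prevents that, and Phase 1 end of study is the end-of-treatment visit anyway.
- A reader might put 48-week PFS at 0.15, 0.22 and 0.30 for 10%, 20% and 30% stopping. Those values arise only if stoppers never die before study end and have no end-of-treatment scan; 6.10, 6.13 and the follow-up schedules say otherwise.
- A reader might take 56 or 63 days as the least possible DOR excess. The imaging schedules allow earlier scans.

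What does not stand is that the text needs no change. The sentence refers to time-to-event endpoints without restriction, DOR is one of them, and for PTCL nothing else supplied fills the gap. A later SAP that does it correctly would depart from the protocol's wording.

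**Conclusion.** The concern holds for Phase 2a only. Followed as written, 7.6 gives DOR the wrong origin, contradicting the combination-cohort endpoint and Appendix K and leaving PTCL with no correct rule. It also runs event-free PFS beyond the last scan.

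The DOR excess equals each responder's time to response, roughly 2 months at the first scheduled scan; this follows from the schedule. The PFS figures, about 0.10–0.17 against about 0.08 at 48 weeks, are illustrative and depend on the assumed median, stopping rates and post-progression survival. The upward direction held throughout the scenarios, and little effect is expected on the median.

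The supplied documents do not show that Phase 2a will actually be analyzed this way. The sentence may have been meant only for OS and PFS, and the Phase 2a SAP was not available to check.

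**What to change.** Replace the sentence in Protocol 7.6 with one paragraph and carry it into the Phase 2a SAP:

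- TTR, PFS and OS start at first dose of ALRN-6924.
- DOR starts at the first documented CR or PR, in all cohorts including PTCL.
- PFS and DOR without an event are censored at the last adequate tumor assessment showing no progression, with the SAP 4.2 rule for two or more consecutive missed assessments.
- OS is censored at the date last known alive.

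This extends the sponsor's own Phase 1 rules to Phase 2a. It needs no new data and no extra visits. The cost is the wording change and somewhat less favourable reported DOR and 1-year PFS.
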